3	900 mg	900 mg	400 mg (micronized)
4	900 mg	900 mg	600 mg (micronized)
5	900 mg	900 mg	800 mg (micronized)
6	900 mg	900 mg	1200 mg (micronized)

Enrollment completed in March 2017 with 75 subjects evaluable for safety and 69 subjects evaluable for efficacy. The MTD was not reached in the CLL (N = 22) or NHL cohort (N = 53). The median age of all subjects was 64 years (range 26 – 86). Subjects had a median of 3 prior therapies, and 57% were refractory to their immediate prior therapy.

Diarrhea was the most prevalent adverse event (60% all grades; 8% G \geq 3), followed by nausea (56% all grades; 4% G \geq 3), fatigue (48% all grades; 3% G \geq 3), neutropenia (32% all grades; 28% G \geq 3), vomiting (31% all grades; 1% G \geq 3), and infusion related reactions (31% all grades; 1% G \geq 3). The median time to onset and resolution of diarrhea was 21 days (range, 1 – 838 days) and 7 days (range, 1 – 191 days), respectively. Diarrhea was Grade 3/4 in 6 subjects. Management of Grade 3/4 diarrhea included dose hold (5 cases) and anti-diarrheal medication (3 cases), and all cases resolved. Biopsy-confirmed colitis was reported in 1 subject, and it was managed with treatment hold and steroids. Other Grade 3/4 events observed in greater than 5% of subjects included pneumonia (8%) and abdominal pain (7%). Grade 3/4 alanine transaminase (ALT) and aspartate transaminase (AST) elevations occurred in 3% and 1% of subjects, respectively. One subject with transaminitis received steroid treatment, and 1 case resolved without intervention. ALT/AST elevations of any grade had a median time to onset of 55 days. Pneumonitis was seen in 2 subjects with a median resolution time of 21 days (range, 15–28 days). Treatment was discontinued due to adverse events in 13% of subjects and 15% of subjects had their umbralisib dose reduced.

Efficacy data from all doses of the U2 regimen based on 68 out of 69 subjects evaluable for efficacy are presented in the waterfall plot below.

Response by histology in subjects receiving therapeutic dose levels and above of umbralisib (\geq 1200mg non-micronized or \geq 600mg micronized) in combination with ublituximab is shown in the following table.

Histology	Response, n/N (%)				
	ORR	CR	PR	SD	PD
All patients	29/57 (51)	12/57 (21)	17/57 (30)	11/57 (19)	17/57 (30)
CLL/SLL	10/15 (67)	2/15 (13)	8/15 (53)	2/15 (13)	3/15 (20)
Aggressive B-NHL	6/22 (27)	3/22 (14)	3/22 (14)	5/22 (23)	11/22 (50)
DLBCL	5/19 (26)	3/19 (16)	2/19 (11)	5/19 (26)	9/19 (47)

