- a. Patients enrolled on the single agent treatment Ublituximab will be assessed for toxicities of special interest for 30 days. The study will be halted prematurely if more than 5 patients experience the following toxicities:
 - Grade 4 Neutropenia
 - Neutropenic Fever
- b. The combination arm of Ublituximab + Umbralisib is of special interest in this study. Patients enrolled on this arm will be assessed for toxicities of special interest for 90 days. The study will be halted prematurely if more than 3 consecutive patients enrolled on the combination arm experience any of the following toxicities:
 - Grade 3 or higher pneumonitis
 - Grade 3 or higher colitis
 - Grade 4 hepatitis
 - Grade 4 rash
 - Other grade 4 unmanageable events attributable to the study treatment.
- c. The study will be halted prematurely if a patient develops progressive multifocal leukoencephalopathy on single agent / combination arm of the study.

Patients will continue to receive study therapy as defined by the schema (4 weekly doses of ublituximab in the single agent treatment and ublituximab plus daily umbralisib for a total of 12 cycles in the combination arm) or until disease progression according to Cheson 2014, unacceptable toxicity, death due to an adverse event that is assessed as related to study treatment (by investigator and/or Sponsor), patient or physician decision to withdraw, or pregnancy, whichever occurs first. The study will end when all patients enrolled have completed planned treatment or the Sponsor decides to end the trial, whichever occurs first.

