5.5 PREMATURE TERMINATION OR SUSPENSION OF STUDY (STUDY STOPPING RULES)

Teleconferences will be held with the study sponsor to exchange findings and unexpected results that may occur in patients participating in this study. The study will be terminated based on toxicity stopping rules as discussed in section 8.5. Any new information suggesting the study intervention may be harmful in study population will be shared with the COMIRB. The principal investigator will discuss any such new information via conference with TG Therapeutics, Inc., and if warranted, may choose to terminate study.

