8.5 STUDY HALTING RULES

Efficacy

Due to the small sample size, there will be no study halting rules based on efficacy.

Toxicity

If any patient experiences death due to an adverse event that is assessed as related to study treatment (by investigator and/or Sponsor), it will lead to temporary hold of study pending review by study team.

Treatment-related mortality: If any patient experiences death due to an adverse event that is assessed as related to study treatment (by investigator and/or Sponsor), it will lead to temporary hold of study pending review by study team. The study will be terminated prematurely if at any point 2 patients experience treatment-related death secondary to the study regimen (Ublituximab and/or umbralisib)

Toxicities of special interest:

a. Patients on the single agent treatment Ublituximab will be assessed for toxicities of special interest for 30 days. The study will be halted prematurely if more than 5 patients experience the following toxicities:

- Grade 4 Neutropenia
- Neutropenic Fever

b. The combination arm of Ublituximab + Umbralisib is of special interest in this study. Patients enrolled on this arm will be assessed for toxicities of special interest for 90 days. The study will be halted prematurely if more than 3 consecutive patients enrolled on the combination arm experience the following toxicities:

- Grade 3 or higher pneumonitis
- Grade 3 or higher colitis
- Grade 4 hepatitis

- Grade 4 rash
- Other grade 4 unmanageable events attributable to the study treatment.

c. The study will be halted prematurely if a patient develops progressive multifocal leukoencephalopathy on single agent / combination arm of the study.

Patients will continue to receive study therapy as defined by the schema (4 weekly doses of ublituximab in the single agent treatment and ublituximab plus daily umbralisib for a total of 12 cycles in the combination arm) or until disease progression according to Lugano response Criteria for NHL (Cheson 2014), unacceptable toxicity, death due to an adverse event that is assessed as related to study treatment (by investigator and/or Sponsor), patient or physician decision to withdraw, or pregnancy, whichever occurs first. The study will end when all patients enrolled have completed planned treatment or the Sponsor decides to end the trial, whichever occurs first

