10 STATISTICAL CONSIDERATIONS

10.1 STATISTICAL AND ANALYTICAL PLANS

Based on overall reporting in low tumor burden FL and MZL, CR rate of at least 30% was achieved when single agent rituximab was used in these subsets.

We assume that Best CR Rates, i.e, CR rates at anytime during therapy—during single agent antibody therapy OR during combination therapy—will increase to 50% as compared to this 30% historical control CR rate. Sample size is determined using inference to a known proportion. Under a null hypothesis of 30% CR rate and an alternative hypothesis of 50%, then given a Type I

error rate of 0.10, a one-sided test, and a sample size of 24, then we have 73% power to detect a difference in complete response rate. Efficacy will be assessed using the proportion of patients who have a complete response. The null hypothesis that the true response rate is 30% will be tested against a one-sided alternative. 95% confidence intervals for the true complete response rate will also be calculated

Twenty-four patients are required for this single-stage design. Assuming 20% screen fail/drop-out rate, 30 patients need to be screened for this study.

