10.4.7 PLANNED INTERIM ANALYSES

No interim analyses are planned for this study.

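### The combination-arm halting rule needs a run of at least 4 consecutive patients with a listed toxicity, so it would seldom trigger at true rates of 20–40%; a cumulative count would do better

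*Combined protocol and SAP*

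**What the plan says.** Section 4.1 lists three toxicity rules besides the one for treatment-related death.

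- **Rule (a), single-agent ublituximab** (grade 4 neutropenia, neutropenic fever; 30 days): "The study will be halted prematurely if more than 5 patients experience the following toxicities". This is a total count with no condition on order.
- **Rule (b), combination** (grade 3 or higher pneumonitis or colitis, grade 4 hepatitis, grade 4 rash, other unmanageable grade 4 events attributable to treatment): "The study will be halted prematurely if more than 3 consecutive patients enrolled on the combination arm experience any of the following toxicities". The observation window is stated as: "Patients enrolled on this arm will be assessed for toxicities of special interest for 90 days".
- **Rule (c)**: a single case of progressive multifocal leukoencephalopathy (PML) halts the study.

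Section 8.5 repeats rule (b) with the same condition: "The study will be halted prematurely if more than 3 consecutive patients enrolled on the combination arm experience the following toxicities". Section 5.5 makes that section the operative one: "The study will be terminated based on toxicity stopping rules as discussed in section 8.5". Section 10.4.7 adds: "No interim analyses are planned for this study". Neither 4.1 nor 8.5 gives a tolerable or intolerable toxicity rate for rule (b), a reason for the consecutive condition, or the chance that the rule would trigger.

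**The concern.** More than 3 consecutive patients means an unbroken run of at least 4. Under such a rule the order of events matters as much as their number, because any event-free patient returns the count to zero. A high but not overwhelming toxicity rate can therefore persist through the whole arm without a halt.

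The protocol itself singles out the combination as being of special interest, yet gives it the stricter form of trigger, while the single-agent rule is a plain count. The events in rule (b) are also of the kind that section 1.2 reports as unexpected and life-threatening with another drug acting on the same pathway. The combination safety data in section 1.1.2 come from previously treated patients and show low rates, so rule (b) matters mainly if toxicity in untreated patients turns out worse than expected. That is the situation in which a halting rule has to work.

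**Working it through.** **Plan's own figure.** Rule (b) has no stated operating characteristics to reproduce. The plan's one probability statement is for the primary test: "error rate of 0.10, a one-sided test, and a sample size of 24, then we have 73% power" (section 10.1). With 11 or more complete responses among 24, the exact binomial gives P(X ≥ 11 | 0.30) = 0.074 and P(X ≥ 11 | 0.50) = 0.729, so the stated 73% is reproduced. It says nothing about rule (b).

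**Inputs.**
- Trigger: a run of at least 4 (sections 4.1 and 8.5).
- Number on combination, n: not stated. Only patients without a CR after induction go on to it (section 6.1.1). Assumed: 24 × (1 − 0.30) = 16.8, about 17, using the 30% historical single-agent CR rate; 24 × (1 − 0.50) = 12 as a low case; 24 as the ceiling.
- True rate p of a listed event: not stated; 10% to 50% shown. Events are taken as independent between patients.
- Rough background from section 1.1.2: pneumonitis ("Pneumonitis was seen in 2 subjects" of 75), colitis in 1 of 75, grade 3/4 ALT elevation in 3%. Sum: 2.7% + 1.3% + 3% = about 7%.

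**Current rule.** Let f(n) be the probability of no run of 4 among n patients. Then f(0) = … = f(3) = 1, f(4) = 1 − p⁴, and for n ≥ 5, f(n) = f(n−1) − (1−p)·p⁴·f(n−5). The chance of a halt is 1 − f(n).

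Example with p = 0.30: p⁴ = 0.0081 and (1−p)·p⁴ = 0.00567. So f(4) = 0.9919, f(8) = 0.9919 − 4 × 0.00567 = 0.9692, and continuing, f(12) = 0.9469. The chance of a halt is 0.053.

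| True rate | n = 12 | n = 17 | n = 24 |
|---|---|---|---|
| 10% | 0.1% | 0.1% | 0.2% |
| 20% | 1.2% | 1.8% | 2.7% |
| 30% | 5.3% | 8.0% | 11.7% |
| 40% | 14.6% | 21.3% | 29.9% |
| 50% | 29.9% | 41.7% | 55.0% |

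An even chance of halting needs a true rate of about 60% (n = 12), 54% (n = 17) or 48% (n = 24).

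The largest number of events possible without a halt is n − floor(n/4): 9 of 12, 13 of 17, 18 of 24.

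**Cumulative alternatives.** A fixed count of c or more uses the binomial tail P(X ≥ c). The stepped count halts at 4 or more events up to patient 12, 5 or more for patients 13–18, and 6 or more for patients 19–24. Its figures come from an exact patient-by-patient recursion for ever crossing the boundary. Entries are for n = 12/17/24.

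| True rate | 4 or more | 6 or more (rule (a)'s cutoff) | Stepped 4/5/6 |
|---|---|---|---|
| 10% | 2.6/8.3/21.4% | 0.05/0.5/2.8% | 2.6/3.5/4.9% |
| 20% | 20.5/45.1/73.6% | 1.9/10.6/34.4% | 20.5/28.5/40.6% |
| 30% | 50.7/79.8/95.8% | 11.8/40.3/77.1% | 50.7/65.0/80.6% |
| 40% | 77.5/95.4/99.7% | 33.5/73.6/96.0% | 77.5/89.1/96.8% |

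At the rough 7% background, the stepped count halts in 0.8/1.0/1.3% of trials.

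**The case against.** **Other oversight would notice.** SAEs are reported within 24 hours and reviewed by the DSMC as they occur. Periodic DSM reports summarise toxicity (section 8.6 says every six or twelve months, section 10.4.5 six-monthly). Regular site meetings discuss significant toxicities, and section 5.5 lets the investigator stop the study on new evidence of harm. For individual patients, grade 3 or higher pulmonary toxicity ends both drugs, and colitis or severe liver injury leads to a delay and a lower umbralisib dose. In a single-site, open-label study of 24 patients, a 30–40% rate of such events would probably not go unaddressed. This stands as mitigation. But none of these measures is a pre-specified numerical threshold for the study, and the death and PML rules cover other events.

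**The 18-of-24 figure is an extreme ordering.** This stands. If that many events fell in random order, the chance of no run of 4 would be 20/220 = 9% for 9 of 12, 15/2380 = 0.6% for 13 of 17 and 84/134,596 = 0.06% for 18 of 24. At a true rate of 75% the rule triggers in 81/92/98% of trials. Those maxima show only what the rule permits; the case rests on the table at 20–40%.

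**The gain depends on the cutoff as well as the form.** This also stands. With rule (a)'s cutoff of 6 and 12 patients, a cumulative rule still triggers only 2/12/34% of the time at 20/30/40%. The stepped count reaches only 21–41% at a 20% rate.

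**The rates are soft.** The protocol names no unacceptable rate, so 20–40% is an assumption. In the 7% sum, pneumonitis and colitis have no stated grade and ALT is grade 3/4, so those parts are upper bounds; rash and other grade 4 events are left out.

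**Timing.** With a 90-day window and accrual that continues during review (section 4.1), any rule may act late. The figures are chances of ever triggering, so they overstate practical protection under both forms.

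**Conclusion.** The concern holds. Rule (b) is the only study-level threshold for these non-fatal combination toxicities. Over 12 to 24 combination patients it would trigger in 1–3% of trials at a 20% rate, 5–12% at 30% and 15–30% at 40%. The stepped cumulative count would trigger in 21–41%, 51–81% and 77–97%.

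This rests on independent events and on assumed arm sizes and toxicity rates, none of which the protocol states. The low sensitivity persists even if all 24 patients receive the combination. The point concerns safety monitoring and does not touch the primary analysis. It should be fixed, but individual protections and DSMC review remain in place meanwhile.

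**What to change.** In sections 4.1(b) and 8.5(b), delete the word consecutive and define the trigger as a cumulative number of combination patients with a listed event, preferably with a threshold that rises with the number treated so far. Add a table of the chance of triggering at acceptable and unacceptable rates for the plausible range of combination patients. The 4/5/6 steps are only an illustration; the cutoff is for the sponsor-investigator and the DSMC to set.

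The cost is amendment wording in two places, one small table, and more false halts if toxicity is in fact acceptable. At a 10% rate these rise from 0.1–0.2% to 2.6/3.5/4.9% (n = 12/17/24) with the stepped count. A fixed count of 4 would cost 2.6/8.3/21%, which is why a rising threshold is preferable.

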4.2 STUDY ENDPOINTS

4.2.1 PRIMARY ENDPOINTS

Efficacy: Best Complete response (CR) rates at anytime during treatment with single agent or combination therapy as defined by the Lugano response Criteria for NHL (Cheson 2014)

4.2.2 SECONDARY ENDPOINTS

Efficacy: To determine Overall response rates (ORR) in the entire cohort as defined by the Lugano response Criteria for NHL (Cheson 2014)

Toxicity:

Ublituximab tolerability as per CTCAE V5.0 criteria

Umbralisib tolerability as per CTCAE V5.0 criteria

5 STUDY ENROLLMENT AND WITHDRAWAL

5.1 INCLUSION CRITERIA

Screening for eligible subjects will be performed within 28 days before study entry unless stated otherwise in the Schedule of Events. Prior to study entry, each potential subject must satisfy all of the following inclusion criteria. Obtaining pathology samples is not required prior to enrollment, but confirmation of availability is required prior to enrollment.

Disease Related

1. Subjects with histologically documented Follicular lymphoma CD20+ (Grade 1, 2 or 3a) *OR* Marginal zone lymphoma CD20+ (nodal, extranodal or splenic) according to World Health Organization (WHO) criteria.
2. Ann Arbor Stage II (Non-contiguous), III or IV disease
3. Patients must have a whole body or limited whole body PET/CT scan performed within 42 days prior to registration. CT portion of PET/CT will be done with contrast based on current NCCN guidelines unless patient has borderline renal function or allergic to contrast dye.
4. Patients must have bone marrow biopsy performed within 6 months prior to registration
5. Measurable node must have an LDi greater than 1.5 cms. In the absence of nodal lesions, measurable extranodal disease should have an LDi greater than 1 cm. In patients with Splenic Marginal Zone lymphoma, in the absence of nodal lesions, spleen size should be over 14 cms with evidence of lymphoma in the bone marrow biopsy.
6. For low tumor burden lymphomas (as determined by GELF criteria)⁷: Include patients diagnosed within 2 years of diagnosis. Low tumor burden patients diagnosed more than 2

years from study entry will be allowed provided patients have documented progression.

Prior Therapy Criteria

1. Patients must be untreated advanced stage disease (Stage III or Stage IV) or Stage II (non-contiguous). (Exception: Involved field or involved site radiation given for localized diagnosis is not considered a line of therapy).

Clinical/Laboratory Criteria

1. Patients must be ≥ 18 years of age and be able to swallow and retain oral medication
2. ECOG performance status of 0-2
3. Patients must have adequate bone marrow function as evidenced by ANC $\geq 1000/\mu\text{L}$ and platelets $\geq 50,000\mu\text{L}$ and Hb $\geq 8\text{g/dL}$ within 28 days prior to registration unsupported by growth factors.
4. Serum creatinine $< 2.0 \text{ mg/dL}$ or calculated creatinine clearance (CrCl) $> 45 \text{ mL/min}$
5. Patients must have adequate hepatic function obtained within 28 days prior to registration and documented by all of the following:
 - Total bilirubin $\leq 1.5 \times \text{IULN}$ ($\leq 5 \times \text{IULN}$ if secondary to lymphoma, Gilbert's syndrome, or medication related)
 - Direct bilirubin $\leq 1.5 \times \text{IULN}$ ($\leq 5 \times \text{IULN}$ if secondary to lymphoma)
 - AST and ALT $\leq 2.5 \times \text{IULN}$ ($\leq 5 \times \text{IULN}$ secondary to lymphoma)
6. Patients must be willing to receive *Pneumocystis jirovecii* prophylaxis with sulfamethoxazole/trimethoprim, dapsone, and atovaquone or inhaled pentamidine, if they initiate combination umbralisib plus ublituximab (not for single agent ublituximab)
7. Patients must have a complete history and physical examination within 28 days prior to registration
8. Patients with follicular lymphoma must have the following components of Follicular Lymphoma International Prognostic Index (FLIPI) available from diagnosis, and collected again at time of registration:
 - Age
 - LDH
 - Number of nodal groups involved
 - Serum or plasma hemoglobin
 - Ann Arbor StageAdditionally, patients must have beta₂-microglobulin collected at time of registration and response assessment.
9. Female subjects of reproductive potential must have a negative serum pregnancy test within 3 days prior to treatment start date. Female subjects who are of non-reproductive potential (i.e., post-menopausal by history - no menses for ≥ 1 year; OR history of hysterectomy; OR history of bilateral tubal ligation; OR history of bilateral oophorectomy at least six weeks ago) are exempt from pregnancy testing. In the case of oophorectomy alone,

only when the reproductive status of the woman has been confirmed by follow up hormone level assessment is she considered not of child bearing potential.

10. Male and female subjects of reproductive potential who agree to use both a highly effective method of birth control (e.g., implants, injectables, combined oral contraceptives, some intrauterine devices [IUDs], complete abstinence, or sterilized partner) and a barrier method (e.g., condoms, cervical ring, sponge, etc.) during the period of therapy.

The following are UNACCEPTABLE forms of contraception for females of childbearing potential:

- natural family planning (rhythm method)
- breastfeeding
- fertility awareness
- withdrawal

For subjects, these birth control requirements must be adhered to for 4 months (120 days) after the last dose of umbralisib or ublituximab, whichever is later.

Regulatory Criteria

1. Patients **must** be informed of the investigational nature of this study and must sign and give written informed consent in accordance with institutional and federal guidelines.

5.2 EXCLUSION CRITERIA

To be enrolled in the study, potential subjects must meet **NONE** of the following exclusion criteria:

Disease-Related

1. Transformed lymphoma; if clinical evidence of transformed lymphoma is present, transformation should be ruled out by biopsy of the suspicious lymph node/lesion
2. Prior treatment for follicular lymphoma or marginal zone lymphoma (Except: involved field or site radiation therapy is allowed)
3. Medically apparent central nervous system lymphoma or leptomeningeal disease
4. Tumor burden where administration of other FDA approved anti-CD20 antibodies like single-agent rituximab would be inappropriate.
5. Patients in need of immediate cytoreduction with chemotherapy based regimen.

Concurrent Conditions

1. Evidence of chronic active Hepatitis B (HBV, not including patients with prior hepatitis B vaccination; or positive serum Hepatitis B antibody) or chronic active Hepatitis C infection (HCV), active cytomegalovirus (CMV), or known history of HIV (or positive HIV test during screening). If HBc antibody is positive, the subject must be evaluated for the presence

of HBV DNA by PCR. If HCV antibody is positive, the subject must be evaluated for the presence of HCV RNA by PCR. See Appendix: HEPATITIS B SEROLOGIC TEST RESULTS. If the subject is CMV IgG or CMV IgM positive, the subject must be evaluated for the presence of CMV DNA by PCR. Subjects with positive HBc antibody and negative HBV DNA by PCR are eligible. Subjects with positive HCV antibody and negative HCV RNA by PCR are eligible (subjects who are CMV IgG or CMV IgM positive but who are CMV DNA negative by PCR are eligible).

2. For subjects with a prior known history of hepatitis B and for those with a positive anti-HBc with negative HBsAg at screening, contraindication or intolerance to antiviral agents effective against hepatitis B.
3. Ongoing drug-induced liver injury, alcoholic liver disease, non-alcoholic steatohepatitis, primary biliary cirrhosis, extrahepatic obstruction caused by stones, or cirrhosis of the liver
4. Inflammatory bowel disease (such as Crohn's disease or ulcerative colitis)
5. Irritable bowel syndrome with greater than 3 loose stools per day as a baseline
6. Active autoimmune disease requiring ongoing immunosuppressive therapy including systemic corticosteroids (prednisone or equivalent ≤ 10 mg daily allowed as clinically warranted) within 12 months prior to enrollment. Patients are allowed to use topical or inhaled corticosteroids or levothyroxine for hypothyroidism or hypoglycemic agents for diabetes mellitus.
7. Any severe and/or uncontrolled medical conditions or other conditions that could affect participation in the study such as:
 - Symptomatic, or history of documented congestive heart failure NYHA (New York Heart Association) functional classification III-IV [see Appendix: New York Heart Association Classifications]
 - Significant cardiovascular disease such as uncontrolled or symptomatic arrhythmias, CHF, or myocardial infarction within 6 months of enrollment.
 - Concomitant use of medication known to cause QT prolongation or torsades de pointes should be used with caution and at investigator discretion.
 - Poorly controlled or clinically significant atherosclerotic vascular disease including cerebrovascular accident (CVA), transient ischemic attack (TIA), angioplasty, cardiac or vascular stenting within 6 months of enrollment.
7. Women who are pregnant or lactating
8. Live virus vaccines within 4 weeks prior to ublituximab therapy, or planned administration of live virus vaccines during ublituximab therapy
9. History of other malignancies (including myelodysplastic syndromes) **except:**
 - malignancy treated with curative intent and with no known active disease present for >2 years before the first dose of study drug and felt to be at low risk for recurrence by treating physician
 - adequately treated non-melanoma skin cancer without evidence of disease
 - adequately treated carcinoma in situ without evidence of disease

- localized prostate cancer and PSA <1.0 mg/dL on 2 consecutive measurements at least 3 months apart with the most recent one being within 4 weeks of study entry

